Rationale for study criteria: The high-risk period for severe mood disorders (SMD) ranges from about 13 – 25 years of age, with the peak age of onset between 14-15 years old. To increase cohesion and participant acceptability within a group treatment, we chose to restrict eligibility to a smaller age range. We decided on the ages of 13-17 years old (essentially the high school age period) for a couple reasons. First, it is important for members within the group to be of similar developmental stage and feel comfortable with one another. Having too large of an age-range within a group treatment (e.g., adolescents with young adults) can be problematic as adolescents face different challenges than young adults. Additionally, content of adult discussion can be inappropriate for adolescents. Second, the primary mentor's ([name]) clinic provides services to children and adolescents, and this clinic serves as one of the primary recruitment sources. Limiting enrollment to individuals with high risk for SMD classifications was based on two main principles. First, individuals with full threshold bipolar disorder or long-standing and unremitting unipolar depression typically require more intensive and disorder-specific treatment. Second, the study questions have largely been tested on individuals with less severe depressive and anxiety disorders. Thus, individuals at high-risk for SMD are uniquely appropriate to address this project's aims. Finally, although speaking English may be a limiting factor for some participants, we have not yet excluded any interested participants from our pilot study based on this criterion. Ensuring that participants share a language with each other is essential for group cohesion and instruction of therapeutic skills. Future grants stemming from this project will include community-based outreach efforts to extend the testing and dissemination of this program to more diverse groups.

Recruitment and screening procedures: *Full details are provided in the Recruitment and Retention Plan.*

Participants will be identified using research databases of patients/former research participants who consented to being contacted for future research studies within UCLA's CHAMP. Additionally, participants may learn about the study through flyers placed throughout outpatient mental health clinics or other UCLA Health System

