research outreach programs. I have budgeted in salary support for a research coordinator two days per week throughout Years 1-4 of the award. The research coordinator will screen all interested participants by phone to assess study eligibility, explain the purpose of the study and study procedures, and answer any questions. For individuals interested and eligible in participating, youth will complete the informed assent process and their parent/guardian will complete the informed consent process (detailed below). In addition to the phone screening of eligibility criteria, an in-person eligibility assessment will be conducted with the PI and research coordinator to assess for DSM/SIPS diagnostic criteria, explain the study procedures in more detail, and answer any questions. Recruitment will be done until there are enough participants to randomize and fill two groups of $n > 6$ per group.

Overview of study activities: Aim 1 will consist of focus groups, followed by an iterative app-development process with an interdisciplinary expert panel, and then an open trial of an app-enhanced cognitive-behavioral treatment (CBT). Focus groups will be held in a conference room at the UCLA Semel Institute and last approximately 60 minutes. The open trial will consist of a pre-treatment assessment, nine 90-minute group treatment sessions, and post-treatment session that includes an exit interview. Aims 2 & 3 will consist of a RCT of the app-enhanced CBT, which will compare nine 90-minutes sessions of the group CBT to nine 90-minute sessions of the app-enhanced group CBT. The RCT will also consist of a pre-treatment assessment, a post-treatment assessment, and a 3-month follow-up assessment following the completion of the group. The open trial and the RCT will be held in group therapy rooms at the UCLA Semel Institute. Finally, I will conduct longitudinal and machine learning analyses of data collected throughout the RCT.

Study Procedures, Materials, and Potential Risks

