The benefits to participants are moderate to high. Participants will have the opportunity to discuss ongoing concerns related to their psychiatric symptoms, including difficulties managing their mood and unusual experiences. Specifically, participants in the groups will have the opportunity to discuss experiences that other peers may not relate to and may even stigmatize. Discussing these experiences and concerns within a group setting provides youth with valuable peer support. This shared experience can help foster self-acceptance, self-efficacy, and emotional validation. Participants engaging in the open trial or the RCT will also be learning evidence-based cognitive-behavioral skills that have been shown to be efficacious for similarly aged youth. Thus, getting exposure to these skills can provide the participants with useful methods of managing stress and coping with their psychiatric symptoms. Additionally, the participants who receive the app-enhanced treatment will have the luxury of readily-accessible psychoeducation and CBT skills on their smartphone. Quick and easy access to psychoeducation and therapeutic skills provides these participants with a beneficial resource that is not commonly available.

Any potential risks to participants, which we believe are minimal, are reasonable and outweighed by these moderate to high potential benefits.

IMPORTANCE OF THE KNOWLEDGE TO BE GAINED

Knowledge Gained

The scientific significant of this study is detailed in the Research Strategy. SMD affects a significant proportion of the population, creating a significant emotional and financial burden on society. Finding ways to intervene effectively in the early stages of SMD is critical. While there are current interventions for the early stages of SMD (most notably CBT), their efficacy is inconsistent and with small effect sizes overall. One proposed reason for the small effect sizes is the low rates of patient compliance to treatment. CBT, as a skills-based

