treatment, is based on the premise that participants need to practice the skills in order to improve. Since participants commonly forget to do the skills, lose their homework assignments, or feel unmotivated to complete the skills, it challenges treatment developers to improve the current treatments and address these barriers to patient compliance. **We propose using a mobile app to improve patient compliance for youth at risk for SMD.** A mobile app can remind participants of skills they need to practice, provide the psychoeducation and skill-practice within the app, and provide contingencies that reward and increase motivation for skill-practice. Additionally, the large amounts of data that a mobile app collects allows for advanced statistical techniques, such as machine learning, to be applied. These efforts can provide a wide range of benefits to youth at risk for SMD and clinical science more broadly. Improving patient compliance can improve treatment outcomes, which reduces burdens on families who face these psychiatric challenges and society at-large who faces this emotional and financial burden. Additionally, through use of machine learning, we can better determine who will and who is benefitting from a skills-based treatment, like CBT. This prediction can help us better tailor treatment recommendations for patients and determine which patients will or will not benefit from a particular type of treatment.

STATISICAL DESIGN AND POWER

Power calculations

For this pilot RCT, we plan to randomize 60 participants to the randomized controlled-trial of the mobile-enhanced treatment. The two treatment groups will be randomized in a 1:1 ratio. Based on pilot trials of this treatment group as well as my primary mentor's ([name]) previous work with interventions for adolescents at high risk for SMI, we anticipate no more than 15-20% dropout by the end of the six-month study. Thus, we expect a final sample size of about 50 with full follow-up (25 in each treatment condition) across 3 assessment time-points (baseline, post-treatment, and three-month follow-up). Actual power will be higher as our general linear mixed modeling allows inclusion of data from subjects with partial data.

Additionally, data collected via the mobile application (app) should greatly increase the number of measurements.

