The power calculation assumes a two-sided significance level, $\alpha=.05$, and a within-subject correlation of $r=.5$ between repeated measures. Under these calculations, for outcomes measures at the three primary assessment time-points, we have 80% power to detect an overall group by time interaction corresponding to a differential treatment effect across the two study arms with an effect size of $f=.30$, just above the above Cohen's threshold for a medium effect ($f=.25$). Thus, recruiting 60 participants will provide ample data for this pilot RCT in order for us to determine initial clinical meaningfulness for the larger grant application to follow this study. However, in accordance with NIMH guidance on the role of pilot RCTs (see: <https://grants.nih.gov/grants/guide/rfa-files/RFA-MH-18-706.html>), this study does not propose to formally assess clinical efficacy or estimates of effect size, due to the unreliability of estimates and limited statistical power yielded from pilot studies.

Statistical analyses

Aim 1 – App acceptability:

- Open trial acceptability: Following the open-trial, we will score participants' rating of app acceptability and treatment satisfaction and burden. We expect high ratings of acceptability (scores>4/5) for the treatment and the app. We will also calculate participant adherence via the extent of weekly practice and percentage of weekly skills practiced. We expect the percentage of weekly skills practiced to be greater than our pilot study as well as the average homework adherence in the literature (>50%).

Aim 2 – Pilot RCT of App-UP:

- Primary Analyses: Treatment conditions will be compared using a general linear mixed modeling (GLMM) approach for the weekly measurements of treatment adherence (both self-report and clinician rated measures) using IBM SPSS software. Time will be based on the standard interval assessments of the study – the baseline, post-treatment, and follow-up assessment). Time, treatment condition, and their interaction will be the primary predictors (controlling for any significant covariates).

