The remaining measures for treatment adherence (i.e., Homework Compliance Scale and Psychosocial Compliance Scale), as well as measures for app acceptability (i.e., Subjective App Usability Scale) and treatment acceptability (i.e., Subjective Treatment Acceptability) will be collected at the post-treatment assessment. Maintenance of treatment adherence will also be collected at the 3-month follow-up assessment. Treatments will be compared on these outcome measures using one-way analysis of variance (ANOVA).

- **Secondary analyses:** Treatment conditions will be compared using a general linear mixed modeling (GLMM) approach for secondary outcome variables (i.e., psychiatric functioning and psychosocial functioning) using IBM SPSS software. Time will be based on the standard interval assessments of the study – the baseline, post-treatment, and follow-up assessment). Time, treatment condition, and their interaction will be the primary predictors (controlling for any significant covariates). Psychiatric symptoms, psychosocial functioning, and emotion regulation (measured continuously) will be the outcome variables for these analyses.

We will also test a mediation analysis, with average participant adherence (measured throughout the study) as the mediator between treatment conditions and the secondary outcome variables. This will be done in two sets of analyses using the SPSS Process macros, which is a statistical package within SPSS that runs bootstrapped mediation analyses. First, the effect of treatment condition, mediated by average treatment adherence, on post-treatment psychiatric and psychosocial functioning will be examined. Second, the effect of treatment condition, mediated by average treatment adherence, on 3-month follow-up psychiatric and psychosocial functioning will be examined.

- **Exploratory analyses:** Two exploratory analyses will be examined. We will make use of the app's big data collection to begin to elucidate the app's effect on participant adherence and clinical outcomes.

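### The one-way ANOVAs on adherence and acceptability treat youths as independent, although both arms are treated in therapy groups (at most about 8 groups in total)

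*Combined protocol and SAP*

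**What the plan says.** Under Overview of study activities, the RCT is described as one "which will compare nine 90-minutes sessions of the group CBT to nine 90-minute sessions of the app-enhanced group CBT". Both arms are therefore delivered in groups. On forming them, the text under Recruitment and screening procedures reads "Recruitment will be done until there are enough participants to randomize and fill two groups of" more than six each.

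Under Statistical analyses, Aim 2, Primary Analyses, the compliance scales, the acceptability scales and the 3-month maintenance of adherence are handled in one sentence: "Treatments will be compared on these outcome measures using one-way analysis of variance (ANOVA". For the mixed models the plan says "Time, treatment condition, and their interaction will be the primary predictors (controlling for any significant covariates", and lists no random effects.

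Under Power calculations, 60 youths are randomized 1:1 and "we expect a final sample size of about 50 with full follow-up (25 in each treatment condition". The plan then says "we have 80% power to detect an overall group by time interaction corresponding to a differential treatment effect across the two study arms", at f = .30. The only correlation assumed there is r = .5 between repeated measures on the same youth. Therapy group, an ICC or a design effect appears nowhere in the analysis or power text.

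**The concern.** Youths who sit through nine sessions together share a leader, a set of peers and a group atmosphere. If that makes their outcomes more alike than those of youths in another group of the same arm, a one-way ANOVA on individuals uses too small an error term for the arm comparison. P-values are then too low, and any intervals reported too narrow. With so few groups, even a small ICC matters, because each arm mean rests on about four group means.

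Only part of the correlation does this. Two groups filled together may share season, recruitment source or referral mix. If one goes to each arm, whatever they share cancels from the difference between arms. The harm comes from the unshared part.

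At stake are the between-arm adherence and acceptability comparisons, which the plan lists as primary and which are meant to inform a larger application.

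**Working it through.** **The plan's own figure.** No power or precision is stated for the ANOVAs. The 80% figure belongs to the group-by-time interaction. With f = .30, m = 3 times and r = .5, it can be matched at N = 60 as a between-arm average test: λ = f²Nm/(1+(m−1)r) = .09×60×3/2 = 8.1, df 1 and 58, power 79.9%. At N = 50, λ = 6.75 and power is 72.1%. The common interaction form, λ = f²Nm/(1−r) = 32.4 at N = 60, gives over 99%. That mismatch of label is a separate matter. What counts here is that none of these forms contains a therapy-group term.

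**Number of groups.** Groups hold at least 7 and are filled in pairs (one per arm, which is inferred). 60/14 = 4.3, so at most 4 pairs, or 8 groups. The size rule is only a lower bound, so there may be fewer.

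**Variance ratio.** Let s be the share of the ICC common to paired groups. With group sizes 7, 7, 8, 8 per arm, the effective size is m = Σmᵢ²/Σmᵢ = 226/30 = 7.53. Relative to independent youths, the variance of the arm difference is about

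1 + (m(1−s) − 1)×ICC.

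With s = 0 this is 1.131, 1.327 and 1.653 at ICC .02, .05 and .10, so 60 youths carry the information of 53, 45 and 36. With s = 1 it is 1 − ICC, below 1. Inflation disappears once m(1−s) ≤ 1, that is, when s is above 1 − 1/7.53, or about 87%.

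**Type I error.** At ICC .05 and s = 0, 2(1 − Φ(1.96/√1.327)) = 8.9%. Simulation of the ANOVA under no arm effect (total variance fixed; simulation error about 0.1 point) gives the following. The ICCs and shares are assumptions.

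| Setting | Share common to pair | ICC .02 | ICC .05 | ICC .10 |
|---|---|---|---|---|
| 60 youths, 8 groups | none | 6.5% | 8.9% | 13.0% |
| | half | 5.6% | 6.7% | 8.5% |
| | three-quarters | 5.3% | 5.6% | 6.4% |
| | all | 4.8% | 4.5% | 4.2% |
| 50 completers, 8 groups | none | 6.3% | 8.2% | 11.4% |
| | half | 5.5% | 6.3% | 7.8% |
| 60 youths, 6 groups of 10 | none | about 7% | 10.5% | about 16% |
| | half | 6.0% | 7.6% | 10.2% |

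**Do the alternatives hold their level?** With 60 youths in 8 groups, a t-test on group means (6 df) gives about 5% with none shared, 3.3 to 4.5% with half, and 1.9 to 4.1% with all. A paired t-test on the group means of each wave (3 df) gives about 5% throughout.

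**Detectable difference.** This is for 25 per arm, 80% power, ICC .05 and none shared. It comes from the noncentral t distribution with standard error √(2/25 × design effect).

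| Analysis | Design effect | df | Critical t | Detectable d |
|---|---|---|---|---|
| Independent youths | 1 | 48 | 2.01 | .81 |
| Group means, 8 groups | 1 + 5.25×.05 = 1.2625 | 6 | 2.45 | 1.07 |
| Group means, 6 groups | 1 + 7.33×.05 = 1.367 | 4 | 2.78 | 1.24 |
| Paired group means, 4 pairs | 1.2625 | 3 | 3.18 | 1.35 |

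**The case against.** The strongest reply is that the documents do not show that outcomes differ between groups within an arm. The eligibility rationale says "To increase cohesion and participant acceptability within a group treatment, we chose to restrict eligibility to a smaller age range", which explains an age limit applied to the whole trial. The benefits section says "Discussing these experiences and concerns within a group setting provides youth with valuable peer support", which would hold in every group. Both make group influence on acceptability plausible, but neither gives its size. This stands: the omission is certain, while its consequence depends on an unknown ICC and an unknown split. In the grid above it runs from slightly conservative to about 16%.

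The second reply is that this is a pilot, and the power section disclaims formal assessment of clinical efficacy and of effect size. That limits the harm. It does not withdraw the between-arm adherence and acceptability tests, which remain planned as primary.

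A reader might also be tempted to carry the point further than the documents allow:

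- **That the 80% power is overstated by a known amount.** The d values above are for one time point and do not correct an interaction at f = .30. A group effect that is constant over time cancels from that interaction.
- **That the mixed models ignore therapy group.** Random effects are unlisted, which is under-specification and does not show that they are excluded. Inflation there needs unshared group effects that arise after baseline.
- **That the mediation analysis is invalid.** Its error rate depends on the size of the mediator-outcome path, which the documents do not give.

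**Conclusion.** The point holds for the one-way ANOVAs. As written, they can give p-values and intervals that are too optimistic, because therapy group is ignored in a design with at most about 8 groups. The effect is small at ICC .02 and material from about .05 if little of the correlation is shared by paired groups. It vanishes if nearly all is shared.

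This rests on one group per arm being filled each time, and on assumed ICCs and shares. It also relies on the group-CBT arms described under Overview of study activities, which match the trial title. The section on telephone screening and consent describes different randomized arms (family psychoeducation with skills training or with supportive individual treatment), and those passages must be reconciled.

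The documents do not support saying that the ANOVAs are certainly inflated, nor any corrected power for the interaction. Severity is modest, given the pilot purpose.

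**What to change.** 1. Keep the ANOVAs as descriptive, and say that they treat youths as independent across therapy groups.
2. Add a between-arm analysis at therapy-group level, and prespecify which version is the reference. A t-test on group means has df equal to the number of groups minus 2, and is valid or conservative. A wave-paired test on group means has df equal to the number of pairs minus 1. It holds 5% whatever the pairs share, but has the least power.
3. Report the estimated ICC with its interval, described as imprecise. With 8 groups and a true ICC of .05, the group variance is estimated at zero in about 36 to 39% of simulated trials.
4. In the mixed models, state the random effects, including whether there is a therapy-group-by-time effect.
5. Note beside the 80% figure that it assumes youths independent across therapy groups.
6. Record each youth's therapy group and wave in the analysis dataset.

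The work is SAP wording and a short extra analysis. The real cost is precision, as in the last table. Part of that is the price of having few degrees of freedom: with 6 df the detectable d is already .95 at ICC 0, against .81.

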Significant symptomatic or functional deterioration. If a participant or family member endorses significant symptomatic or functional deterioration at any point throughout the study protocol or if study staff witness significant deterioration, the participant will be encouraged to seek services with ancillary psychosocial and/or psychopharmacological therapy. Study staff will make every effort to continue to include the participant in the study protocol and participants will be continued in the treatment if they continue to consent to treatment, can tolerate the study protocol, and are not a disturbance to the group setting of the treatment. In cases where the patient requires hospitalization, can no longer tolerate the study protocol, or become a disturbance to the group, the participant will be withdrawn from the study.

Participants will have been informed of these rules during the recruitment phase of the study, both through information given orally and via our informed consent procedures. We will make clear that discontinuing participation in the study will in no way jeopardize their access to other treatments provided by outpatient or inpatient services at the study site. Whenever possible, we will continue to follow these adolescents/YAs using the research outcome battery so that they can be included in intent-to-treat analyses.

Reporting Adverse Events

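### A separate one-way ANOVA of adherence at 3 months ignores the post-treatment scores of youths missing at that visit; scales collected at both visits belong in the mixed model already planned.

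*Combined protocol and SAP*

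**What the plan says.** In Statistical analyses, Aim 2, Primary Analyses, weekly adherence goes to a general linear mixed model. The Homework Compliance Scale, the Psychosocial Compliance Scale and the app and treatment acceptability scales are placed at the post-treatment assessment. The plan adds: "Maintenance of treatment adherence will also be collected at the 3-month follow-up assessment". It then closes the paragraph with: "Treatments will be compared on these outcome measures using one-way analysis of variance (ANOVA". No analysis set and no rule for missing scores is given for these outcomes, and the 3-month instrument is not named.

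Two statements elsewhere bear on this. Power calculations says of the mixed model: "Actual power will be higher as our general linear mixed modeling allows inclusion of data from subjects with partial data". The paragraph on significant deterioration, under the circumstances for study withdrawal, says that youths who leave will be followed where possible "so that they can be included in intent-to-treat analyses".

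**The concern.** A one-way ANOVA by arm at a single visit can use only the scores from that visit. For a scale measured at two visits, a youth seen at post-treatment but not at 3 months contributes nothing to the 3-month comparison, although the earlier score is informative about the missing one. The benefit of partial data that the plan describes for its mixed model therefore does not reach this comparison.

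This could matter more for adherence than for most outcomes. The Noncompliance paragraph withdraws youths for missed sessions or refused follow-up interviews, so missing scores may be tied to the quantity being measured. The app is meant to raise compliance, so dropout could also differ by arm. What is at stake is the between-arm estimate of maintained adherence, which sits under the primary analyses and would inform the larger application to follow.

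**Working it through.** **Inputs from the plan (Power calculations).** "we plan to randomize 60 participants to the randomized controlled-trial of the mobile-enhanced treatment"; "The two treatment groups will be randomized in a 1:1 ratio", so 30 per arm; "we anticipate no more than 15-20% dropout by the end of the six-month study"; "we expect a final sample size of about 50 with full follow-up (25 in each treatment condition"). The within-subject correlation is 0.5 and the effect size is f = 0.30, which for two arms is d = 2f = 0.60.

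**Reproducing the plan's figure.** 60 × 0.85 = 51 and 60 × 0.80 = 48, which agrees with about 50.

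**Assumptions not in the plan.** The true difference is 0.5 SD. Post-treatment scores are complete. Dropout before 3 months follows a logistic function of the post-treatment score, with a slope of 0.5 to 1.5 per SD. The correlation r between visits is 0.5 to 0.7; the plan gives 0.5 for its power calculation, not for adherence in particular. Missing rates by arm (control versus app) are 20% v 10% or 25% v 5%. Each pair averages 15%, inside the plan's dropout range.

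**Bias of the 3-month ANOVA.** Let s(p) be the amount, in SD, by which the mean post-treatment score of those still observed exceeds the mean of the whole arm when a proportion p is missing. Then

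bias = r × [s(app) − s(control)].

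Numerical integration of the logistic model over a normal score gives:

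| Slope | s(5%) | s(10%) | s(20%) | s(25%) |
|---|---|---|---|---|
| 0.5 | 0.025 | 0.049 | 0.096 | 0.120 |
| 1.0 | 0.047 | 0.091 | 0.173 | 0.213 |
| 1.5 | 0.065 | 0.122 | 0.227 | 0.277 |

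Example, slope 1, r = 0.5, 20% v 10%: 0.5 × (0.091 − 0.173) = −0.041 SD.

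| Missing, control v app | r = 0.5 | r = 0.7 |
|---|---|---|
| 20% v 10% | −0.024 to −0.052 | −0.033 to −0.073 |
| 25% v 5% | −0.047 to −0.106 | −0.066 to −0.148 |

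Simulation of the same scenarios reached −0.08 in the first row and −0.15 in the second, so the rounded outer ranges are 0.02 to 0.08 and 0.05 to 0.15 SD. If the app arm loses more, the signs reverse. If both arms lose the same proportion under the same slope, s(app) = s(control) and the bias is 0. An analysis that uses the post-treatment score gave a bias of about 0 in every case.

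**Does unequal dropout need an arm-specific cause?** Not if adherence itself differs. Apply one logistic rule to both arms with 16.7% missing overall (10 of 60) and a true difference of 0.5 SD. At slope 1, 19.7% of control and 13.6% of app youths are then missing, and the bias is −0.025 (r = 0.5) or −0.035 (r = 0.7). Over slopes 0.5 to 1.5 and both values of r, the bias runs from −0.01 to −0.06 SD.

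**Precision.** With equal dropout, 25 of 30 scored per arm at 3 months and r = 0.5, the effective number per arm when post-treatment scores are used is

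1 / [(1 − r²)/25 + r²/30] = 1 / (0.75/25 + 0.25/30) = 26.1.

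Power at d = 0.60 (two-sided 5% t test) rises from 54.7% to 56.6%, about 2 points. Over r = 0.3 to 0.7 and 24 to 25.5 scored per arm, power with the post-treatment score is 53.8% to 58.9%.

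**Scales collected once.** A mixed model on one visit uses the same scores as the ANOVA, so nothing is gained.

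**The case against.** The strongest reply is that the comparison is minor and the bias is small beside the noise. The standard error of a difference with 25 per arm is √(2/25) = 0.28 SD. With 30 randomised per arm, slope 1 and 20% v 10% missing, the root mean square error was 0.277 for ANOVA and 0.276 with the post-treatment score at r = 0.5, and 0.280 v 0.270 at r = 0.7. Even at 25% v 5% it was 0.290 to 0.301 v 0.274 to 0.277. If control loses more, the bias is toward no difference. The plan itself expects 25 per arm and says that this pilot will not formally assess efficacy or effect size. Weekly adherence already goes to a mixed model. All of this stands, and it keeps the point minor.

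Two further limits stand. The 3-month measure is not named; if it is a different instrument, a two-visit model does not apply. Youths withdrawn after a run of missed sessions leave during treatment; if they are not followed, both scores are missing and the change does not help them.

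A reader might infer more than the documents support:

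- **That the ANOVA is restricted to completers.** The plan does not say so. An ANOVA at a visit includes everyone scored then, including youths who stopped treatment but were followed.
- **That it breaks an intent-to-treat commitment.** ANOVA by randomised arm is compatible with intent-to-treat, and the plan intends to follow leavers for that purpose.
- **That the partial-data statement is contradicted.** That statement is confined to the mixed model and makes no promise for the ANOVA outcomes.

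**Conclusion.** The point holds as a modest choice-of-method issue, limited to adherence scales that are collected at both post-treatment and 3 months. For those, a separate 3-month ANOVA discards usable information. Under the stated assumptions it is biased by about 0.02 to 0.08 SD at 20% v 10% missing and 0.05 to 0.15 SD at 25% v 5%, with the direction set by which arm loses more. With equal dropout the bias is about 0 and the cost is about 2 points of power at r = 0.5. These figures rest on an assumed dropout model, assumed missing rates by arm and complete post-treatment scores. The documents neither predict unequal dropout nor exclude it. No stated decision of the pilot would change, but the better method is already in the plan.

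**What to change.** Amend the ANOVA paragraph of the Aim 2 primary analyses as follows:

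1. Name the adherence scale or scales collected at 3 months.
2. For each scale collected at both visits, use the planned mixed model with the post-treatment and 3-month values as repeated measures and arm, visit and their interaction as fixed effects. Leave the covariance of the two visits unstructured.
3. Include every randomised participant with at least one score, analysed as assigned, and report the arm difference with its confidence interval at each visit.
4. Keep one-way ANOVA for scales collected once.
5. Report the number missing at each visit by arm, and the number missing at both, since the model cannot recover the latter. As withdrawal can follow from noncompliance, add a simple sensitivity analysis for them.

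The cost is a few sentences in the analysis plan and the same SPSS procedure, with no extra data collection if the 3-month scale is the same instrument. The model relies on missingness at 3 months being explained by arm and the post-treatment score, which is a weaker assumption than the ANOVA needs.
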